9.2 Laboratory Correlative Studies

Genome and Transcriptome Sequencing

Pretreatment tumor biopsy or archival specimen will undergo sequencing would as part of the **OSU Precision Cancer Study** (OSU-13053), a companion study to this trial. This study supervises collection of research tumor biopsies/archival specimens, germline tissue collection (blood, buccal swabs), genomic sequencing strategies, and return of results. This study shares data and samples for patients who subsequently participate in a therapeutic study such as this Phase 2 ponatinib trial. An integrative sequencing strategy, clinical and research would be utilized for this study. Clinical sequencing would be performed in CLIA-certified lab ([name] Lab) for a custom cancer panel of 220 genes. Research sequencing includes whole exome and transcriptome sequencing (RNASeq) of tumor to identify potentially informative mutations, amplifications, or gene fusions to evaluate for biomarkers of sensitivity and mechanisms of resistance. The custom cancer panel includes assessment of both DNA and RNA for 220 oncogenes (including *FGFR1*, *FGFR2*, *FGFR3*, and *FGFR4*) and tumor suppressors and is designed to detect point mutations, copy number changes, and gene fusions. The list of genes is shown in Figure 3.

A similar study is in place at University of Michigan (MI-ONCOSEQ/HUM00067928; PI- [name]) that supervises collection of research tumor biopsies/archival specimens, genomic sequencing strategies, and return of results. This study would screen and identify patients with tumors that harbor activating genomic alterations in *FGFR* (mutations, amplifications, fusions) and other genomic alterations (*KIT*, *RET*, *PDGFR α* , *ABL1* and *FLT3*) for enrollment at University of Michigan.

CLIA Sequencing: Targeted gene sequencing is accomplished by solution-based hybridization capture with custom baits (Agilent) of both tumor (biopsy or archival specimen) and normal DNA (Blood). This is used to generate somatic point mutations and copy number changes using published tools (VarScan2, MuTect)^{45, 48}. Targeted gene sequencing from RNAseq libraries is utilized to identify gene fusions involving FGFRs and analyzed using published fusion tools (Tophat2, Chimerascan)^{49, 50}. All sample collection, processing, sequencing, and analysis will be completed in [name] CLIA-certified lab.

Research Sequencing: For research sequencing, we would use Agilent's SureSelect whole exome capture and Illumina's TruSeqRNA protocols to prepare libraries for sequencing as previously described.⁴⁵ Libraries will be submitted to a vendor for sequencing on an Illumina HiSeq2000 instrument (Beijing Genomics Institute). Bioinformatics analysis will be performed in the lab to derive annotated single nucleotide variation, copy number alterations, and gene expression using existing tools as previously described (Exome: BWA, VarScan2, MuTect; RNAseq: Tophat2, Cufflinks).⁴⁵

ABL1	CDK4	ESR1	FLT4/VEGFR3	MAP2K4	PAK7	ROCK1
ABL2	CDK6	EZH2	FOXL2	MAP3K1	PALB2	RPA1
AKT1	CDK8	FANCA	GNA11	MAP3K13	PAX5	RPTOR
AKT2	CDKN1B	FANCC	GNAQ	MCL1	PDGFRA	RUNX1
AKT3	CDKN2A	FANCD2	GNAS	MDM2	PDGFRB	SETD2
ALK	CDKN2B	FANCE	GRIN2A	MDM4	PDK1	SF3B1
APC	CDKN2C	FANCF	HGF	MEN1	SOX2	SH2B3
AR	CEBPA	FANCG	HRAS	MET	PIK3C2G	SMAD2
ARAF	CHEK1	FANCL	HSP90AA1	MITF	PIK3C3	SMAD3
ARID1A	CHEK2	FBXW7	IDH1	MLH1	PIK3CA	SMAD4
ASXL1	CHUK	FGF1	IDH2	MLST8	PIK3CG	SMO
ATM	CRBN	FGF10	IGF1	MPL	PIK3R1	SPOP
ATR	CREBBP	FGF12	IGF1R	MRE11A	PIK3R2	SRC
AURKA	CRKL	FGF14	IGF2R	MSH2	STK12	STAT3
AURKB	CRLF2	FGF17	IKBKE	MSH6	SUFU	STAT4
AXL	CTNNA1	FGF18	IKZF1	MTOR	PRDM1	STK11
BACH1	CTNNB1	FGF19	INHBA	MYC	PRKAR1A	TET2
BAP1	CYP17A1	FGF2	INSR	MYCN	PRKDC	TGFB2
BARD1	DDR2	FGF22	IRF4	MYD88	PTCH1	TNKS
BCL2	DNMT3A	FGF23	JAK1	NCOR1	PTCH2	TNKS2
BCL2A1	DOT1L	FGF3	JAK2	NF1	PTEN	TOP1
BCL2L1	EGFR	FGF4	JAK3	NF2	PTK2	TP53
BCL2L2	EPHA3	FGF5	JUN	NFKB1	PTK2B	TRRAP
BCL6	EPHA5	FGF6	KDR/VEGFR2	NFKBIA	PTPN11	TSC1
BLM	EPHA6	FGF7	KIT	NOTCH1	PTPRD	TSC2
BRAF	EPHA7	FGF8	KRAS	NOTCH2	RAD50	TYK2
BRCA1	EPHB1	FGF9	LRP1B	NOTCH3	RAD51	VHL
BRCA2	EPHB4	FGFR1	LRP6	NOTCH4	RAF1	WT1
CARD11	EPHB6	FGFR2	LRRK2	NRAS	RARA	
CCND1	ERBB2	FGFR3	LTK	NTRK1	RB1	
CCND2	ERBB3	FGFR4	MAGED1	NTRK2	RET	
CCND3	ERBB4	FLT1/VEGFR1	MAP2K1	NTRK3	RHEB	
CCNE1	ERG	FLT3	MAP2K2	PAK3	RICTOR	

Figure 3: Gene Panel List

Reverse Phase Protein Assay (RPPA)

In addition to genome and transcriptome sequencing we would also perform RPPA to assess protein expression and modifications that characterize canonical pathways in cancers. This assay will be run at MD Anderson Cancer Center RPPA-Functional Proteomics Core Facility.

Sections of the OCT embedded core biopsies/archival tumor specimens will be evaluated by a pathologist to verify tumor content. Tissue will then be cut out of the OCT and protein will be extracted using standard methods. The protein will be denatured, diluted and arrayed on nitrocellulose coated slides. The slides will be probed with a set of over 200 validated antibodies and spot density determined by MicroVigene software. Samples will be normalized for protein loading and concentrations will be determined using the Super Curve Fitting program.

Supervised and un-supervised hierarchical clustering analysis will then be performed. Some of the proteins of interest that are included in this assay are; PI3KCA, total and phosphorylated forms of Akt, mTOR, Cyclin D1, ERK, MEK, p70-S6 kinase etc. RPPA data at the time of

disease progression to ponatinib would be compared with data prior to treatment with ponatinib to evaluate for putative mechanisms of resistance to FGFR targeting.

Data Integration: Using the exome sequencing, transcriptome sequencing, and RPPA, we can systematically characterize candidate mechanisms of resistance in the FGFR pathway at the time of disease progression with ponatinib. Putative changes of interest would likely include splice variants in FGFR, increased FGFR gene expression, point mutations or copy number variation in FGFR signaling pathways (PI3-kinase or MAP kinase).

9.3 Specimen Storage and Disposal

Specimens will be stored in designated and secure facilities at The Ohio State University. The Precision Cancer Study uses a secure Custom Database/LIMS to catalog, store, and track specimens. The Study stores specimens in monitored and locked freezers that are in a secure facility.

Generally, frozen tissue will be stored in secured -80°C freezers. Storage and retrieval of fixed and paraffin embedded specimens will be handled using routine procedures of the Pathology Department affiliated with the hospital at which the specimen was collected. Disposal of biospecimens will be considered under certain circumstances including but not limited to reduced specimen integrity, exhausted capacity or insufficient funds for long-term maintenance or storage of low priority biospecimens. Determination of the integrity and priority of biospecimens is at the discretion of study personnel. The discarding of research specimens is also subject to any institutional policy and the informed consent under which the specimen was obtained.

9.4 Sites Performing Correlative Studies

- Integrated sequencing analysis (exome and transcriptome sequencing) would be performed at The Ohio State University ([name] Lab) and University of Michigan ([name]'s Lab). Methodologies for exome and transcriptome sequencing are identical.
- The RPPA assay will be performed by MD Anderson Cancer Center RPPA-Functional Proteomics Core Facility.

9.5 Potential risks and procedures for minimizing risks

9.5.1 Risks of blood draws

All blood draws will be performed by trained personnel that use standard sterile techniques. Infection is unlikely since stringent aseptic techniques are followed during all venipuncture procedures.

9.5.2 Risks of biopsy

The risks of this study relate primarily to the risk of a biopsy. In general, these procedures are associated with a small risk of pain, bleeding, infection, and damage to adjacent organs. The magnitude of this risk depends somewhat upon the site of the procedure. Potential risks according to site are:

Risks of core breast biopsy:

- Likely: local discomfort and minor bleeding.
- Less likely: moderate or major bleeding, need for blood transfusion, hospitalization due to bleeding or other complications, infection, pneumothorax, damage to adjacent organs.

Risks of skin/chest wall punch biopsy:

- Likely: local discomfort and minor bleeding.
- Less likely: moderate or major bleeding, or infection

Risks of lymph node or soft tissue core needle biopsy:

- Likely: local discomfort and minor bleeding.
- Less likely: moderate or major bleeding, need for blood transfusion, hospitalization due to bleeding or other complications, infection, pneumothorax, damage to adjacent organs.
- Additional risks may be present if i.v. conscious sedation is required.

Risks of liver core needle biopsy:

- Likely: local discomfort and minor bleeding
- Less likely: moderate or major bleeding, need for blood transfusion, hospitalization due to bleeding or other complications, infection, bowel perforation or damage to adjacent organs
- Additional risks may be present if i.v. conscious sedation is required.

Lung biopsy core needle biopsy:

- Likely: local discomfort and minor bleeding
- Less Likely: moderate or major bleeding, need for blood transfusion, lung collapse, hospitalization due to bleeding or other complications, infection, damage to nearby organs, allergic reaction to the numbing medicine

Bone Marrow Biopsy:

- Likely: local discomfort and minor bleeding
- Less Likely: Nerve injury, blood collection at the site

In order to minimize the risk of a biopsy, only qualified personnel will perform these procedures. Prior to the procedure, the physician performing the procedure will discuss the risks with each study participant, answer any questions, and obtain separate procedure consent. For biopsies of lesions that are not superficial and clearly palpable, imaging studies such as CT, ultrasound, or MRI will be used to guide the biopsy in order to minimize the risk of damage to adjacent structures. After lymph node biopsies, patients will be observed for approximately 2 hours (range 2-4 hours) after the procedure, or per institutional standard guidelines. After liver biopsies,

patients will be observed for approximately 4 hours (range 4-6 hours) after the procedure, or per institutional standard guidelines. Less than the goal quantity of tissue is acceptable for each type of biopsy, and will be left to the clinical judgment of the physician performing the procedure.

All grade 3 or 4 events attributable to any of the study procedures will be reported to the Principal Investigator within 24 hours of occurrence. Adverse events will be reported by the PI to the IRB consistent with standard procedures.

9.5.3 Anesthesia Risk

Risks of local anesthesia

All biopsy procedures require local anesthesia using lidocaine, xylocaine, or related compounds. There is a small risk of an allergic reaction associated with these drugs.

In order to minimize the risk of local anesthesia, only qualified personnel will perform the biopsy procedure. Patients will be queried if they have had previous allergic reactions to local anesthetics.

Risks of intravenous conscious sedation

Certain biopsy procedures, such as lymph node or liver biopsies, may require intravenous conscious sedation (IVCS). IVCS is a minimally depressed level of consciousness that retains the patient's ability to maintain a patent airway independently and continuously and respond appropriately to physical stimulation and verbal commands.

The risks of intravenous conscious sedation include: inhibition of the gag reflex and concomitant risk of aspiration, cardiopulmonary complications (myocardial infarction, cardiac arrhythmias, hypoxemia), and allergic reactions to the sedative or analgesic medications. These risks are small but real; for example, in a prospective study of 14,149 patients undergoing IVCS during upper gastrointestinal endoscopies, the rate of immediate cardiopulmonary events was 2 in 1000. The 30-day mortality was 1 per 2,000 cases. In this study, there was a strong association between lack of monitoring and use of high-dose benzodiazepines with adverse outcomes. There was also an association between the use of local anesthetic sprays to the oropharynx and the development of pneumonia.

In order to minimize the risk of intravenous conscious sedation, only qualified personnel will be responsible for conscious sedation as per institutional protocols. A minimum of two individuals will be involved in the care of patients undergoing conscious sedation—the physician performing the biopsy procedure, and the individual (M.D. or R.N.) who monitors the patients and his/her response to both the sedation and the procedure, and who is capable of assisting with any supportive or resuscitative measures. The room where the procedure utilizing IVCS takes place will have adequate equipment to provide supplemental oxygen, monitor vital signs, and maintain an airway should this be necessary. An emergency cart will also be immediately accessible to the room where the procedure is to take place, and emergency support services will be available on page. Patients will be screened and evaluated for their fitness to undergo conscious sedation

by a trained physician. Following the procedure, patients will be observed closely in the recovery room according to standard institutional guidelines.

9.5.4 Risk of imaging studies

Some biopsy procedures require imaging studies, either to plan or guide the procedure. Imaging studies that may be used in obtaining tissue samples include CT scans and ultrasound. CT scans will expose study participants to controlled amounts of radiation. The total dose of radiation from these tests is not anticipated to cause any adverse effects. There is also a risk of an allergic reaction to the intravenous contrast dye used during CT imaging, as well as a risk of experiencing feelings of anxiety or claustrophobia while undergoing a CT scan. There are no anticipated risks with the use of ultrasound.

In order to minimize these risks, patients will be queried, as per standard institutional practice, regarding their history of reactions to intravenous contrast dye. If a patient has had such a reaction, she/he will be premedicated, or dye will not be used, as per standard institutional practice. If a patient has previously experienced anxiety or claustrophobia while undergoing a CT scan, anxiolytics may be considered as indicated.

10. STUDY CALENDAR

Baseline evaluation must be conducted within 2 weeks prior to start of ponatinib therapy. Imaging studies must be done \leq 4 weeks prior to the start of therapy. In the event that the patient's condition is deteriorating, laboratory evaluations should be repeated within 48 hours prior to initiation of the next cycle of therapy. Appropriate delays in study treatment or procedures are allowed to adjust for holidays or weekends. Each cycle is **28** days.

Study Assessment ^{s¹}	Screen	During Ponatinib Therapy		Final Study Visit ³	Follow-Up ⁹
Informed Consent	X				
Baseline Demographics	X				
Ophthalmic Exam ²	X	As clinically indicated			
Medical History / Interim History	X	Day 1 (\pm 3 days) of each cycle		X	
Concomitant Medications	X	Continuous			
Physical Exam	X	Day 1 (\pm 3 days) of each cycle		X	
ECOG Performance Status	X	Day 1 (\pm 3 days) of each cycle		X	
Vital Signs (BP, HR, Temperature, weight)	X	Day 1 (\pm 3 days) of each cycle		X	
Blood Pressure (at home) ⁴		Twice per week during cycle			
Chemistry ⁵	X	Day 1 (\pm 3 days) of each cycle		X	
Triglycerides	X				
CBC, Diff, Plt	X	Every 2 weeks for first 2 cycles	Day 1 (\pm 3 days) from cycle 3		
Liver Function Testing		Cycle 1 Day 1	Once per month, or more frequent if clinically indicated		
Serum Amylase, Serum Lipase	X	Every 2 weeks for first 2 cycles	Day 1 (\pm 3 days) from cycle 3		
Pregnancy Test ⁶	X				
12-Lead ECG	X	Repeated as Clinically Indicated			
LVEF (ECHO)	X	Repeated every 3 cycles \pm 7 days or as Clinically Indicated			
Research Biopsy(s) ⁷	Research biopsies on eligible	Research biopsies will be attempted on all patients at time of progression			

	patients prior to the study			
Study Agents		Ponatinib will be administered daily		
Tumor measurement S ⁸	X	Staging will occur after every 2 cycles \pm 7 days or as Clinically Indicated		
Adverse Events		Continuous		

1. Assessments scheduled on days of dosing must be done prior to administration of study drug(s), unless otherwise specified.
2. Ophthalmic exam will include indirect and direct fundoscopy, visual acuity, visual field examination, tonometry and color fundus photos. Additional ophthalmic exams will be performed if symptomatically warranted.
3. Final Study Visit must occur 21 days (\pm 7 days) after last dose of study drug.
4. Blood pressure cuff will be provided by Takeda. Patients will record readings in diary (Appendix B) and bring with them to clinic visits.
5. Including alkaline phosphatase, total bilirubin, albumin, creatinine, glucose, potassium, SGOT, SGPT, sodium, magnesium, chloride, bicarbonate, phosphate.
6. Perform only in women of child-bearing potential.
7. Research biopsies will be performed as part of the OSU Precision Cancer Trial (or through MI-ONCOSEQ for study enrollment at University of Michigan). Blood, buccal samples must also be obtained per **Section 9**.
8. Radiologic documentation must be provided for patients removed from the study due to progressive disease for solid tumors. CT chest/abdomen/pelvis is preferred. Bone scan, MRI or PET may be used at the discretion of treating physician.
9. Patients discontinuing for toxicity are followed until resolution of the toxicity, as outlined in **Section 5.4**. Patients who have discontinued protocol therapy will be followed every 3 months for 52 weeks or until death, whichever occurs first, in order to document time of progression (if patient did not progress while on study), survival, and to document subsequent alternate therapy received. For patients with resolution of toxicity to protocol therapy, telephone follow-up is permitted.

11. MEASUREMENT OF EFFECT

11.1 Antitumor Effect – Solid Tumors

For the purposes of this study, patients should be re-evaluated for response every 8 weeks. In addition to a baseline scan, confirmatory scans should also be obtained 8 weeks following initial documentation of objective response.

Response and progression will be evaluated in this study using the new international criteria proposed by the revised Response Evaluation Criteria in Solid Tumors (RECIST) guideline (version 1.1) [Eur J Ca 45:228-247, 2009]. Changes in the largest diameter (unidimensional measurement) of the tumor lesions and the shortest diameter in the case of malignant lymph nodes are used in the RECIST criteria.

11.1.1 Definitions

Evaluable for toxicity. All patients will be evaluable for toxicity from the time of their first treatment with ponatinib

Evaluable for objective response. Only those patients who have measurable disease present at baseline, have received at least one cycle of therapy, and have had their disease re-evaluated will be considered evaluable for response. These patients will have their response classified according to the definitions stated below. (Note: Patients who exhibit objective disease progression prior to the end of cycle 1 will also be considered evaluable)

Evaluable Non-Target Disease Response. Patients who have lesions present at baseline that are evaluable but do not meet the definitions of measurable disease, have received at least one cycle of therapy, and have had their disease re-evaluated will be considered evaluable for non-target disease. The response assessment is based on the presence, absence, or unequivocal progression of the lesions.

11.1.2 Disease Parameters

Measurable disease. Measurable lesions are defined as those that can be accurately measured in at least one dimension (longest diameter to be recorded) as ≥ 20 mm by chest x-ray or as ≥ 10 mm with CT scan, MRI, or calipers by clinical exam. All tumor measurements must be recorded in millimeters (or decimal fractions of centimeters).

Note: Tumor lesions that are situated in a previously irradiated area may be considered measurable.

Malignant lymph nodes. To be considered pathologically enlarged and measurable, a lymph node must be ≥ 15 mm in short axis when assessed by CT scan (CT scan slice thickness recommended to be no greater than 5 mm). At baseline and in follow-up, only the short axis will be measured and followed.

Non-measurable disease. All other lesions (or sites of disease), including small lesions (longest diameter <10 mm or pathological lymph nodes with ≥ 10 to <15 mm short axis), are considered non-measurable disease. Bone lesions, leptomeningeal disease, ascites, pleural/pericardial effusions, lymphangitis cutis/pulmonitis, inflammatory breast disease, and abdominal masses (not followed by CT or MRI), are considered as non-measurable.

Note: Cystic lesions that meet the criteria for radiographically defined simple cysts should not be considered as malignant lesions (neither measurable nor non-measurable) since they are, by definition, simple cysts.

‘Cystic lesions’ thought to represent cystic metastases can be considered as measurable lesions, if they meet the definition of measurability described above. However, if non-cystic lesions are present in the same patient, these are preferred for selection as target lesions.

Target lesions. All measurable lesions up to a maximum of 2 lesions per organ and 5 lesions in total, representative of all involved organs, should be identified as **target**

lesions and recorded and measured at baseline. Target lesions should be selected on the basis of their size (lesions with the longest diameter), be representative of all involved organs, but in addition should be those that lend themselves to reproducible repeated measurements. It may be the case that, on occasion, the largest lesion does not lend itself to reproducible measurement in which circumstance the next largest lesion which can be measured reproducibly should be selected. A sum of the diameters (longest for non-nodal lesions, short axis for nodal lesions) for all target lesions will be calculated and reported as the baseline sum diameters. If lymph nodes are to be included in the sum, then only the short axis is added into the sum. The baseline sum diameters will be used as reference to further characterize any objective tumor regression in the measurable dimension of the disease.

Non-target lesions. All other lesions (or sites of disease) including any measurable lesions over and above the 5 target lesions should be identified as **non-target lesions** and should also be recorded at baseline. Measurements of these lesions are not required, but the presence, absence, or in rare cases unequivocal progression of each should be noted throughout follow-up.

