3.2.23 Patients on medications known to be associated with Torsades de Pointes

- 3.2.24 Patients who received the last administration of an anti-cancer therapy including, chemotherapy, immunotherapy/biologic therapy, targeted therapy or radiotherapy within 4 weeks (6 weeks for nitrosoureas or mitomycin C) or within 5 half-lives, whichever is shorter, prior to entering the study.
- 3.2.25 Patients who have not recovered (\leq CTCAE grade 1) from adverse events (with the exception of alopecia) due to agents administered more than 4 weeks earlier.
- 3.2.26 Patients taking medications or herbal supplements that are known to be strong CYP3A4 inhibitors within at least 14 days prior to registration are excluded
- 3.2.27 Patients with symptomatic or progressive brain metastases are ineligible. Subjects with treated brain metastases are eligible if they have no radiographic or other signs of progression in the brain for \geq 4 weeks after completion of local therapy.
- 3.2.28 Patients with macular edema, retinal vein occlusion or retinal hemorrhage are excluded.
- 3.2.29 Patients who have received prior FGFR targeted therapy.

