4. REGISTRATION PROCEDURES

4.1 General Guidelines

Eligible patients will be entered on study centrally at the *The Ohio State University*. OSU patients will be registered by the OSU Clinical Research Specialist/Coordinator. External participating site patients will be registered by the OSU Multi-Site Coordinator. External sites should alert the Multi-Site Coordinator by e-mail or phone as soon as a potential patient is identified for screening. The required registration forms can be found in the protocol Supplemental Forms packet.

Following registration, patients should begin protocol treatment within 5 business days. Issues that would cause treatment delays should be discussed with the Principal Investigator. If a patient does not receive protocol therapy following registration, a written explanation documenting the reason for delay will be required before proceeding with therapy. The Multi-Site Coordinator should be notified of any cancellations as soon as possible. The patient's registration may be cancelled, pending approval by the Principal Investigator who will determine whether the patient will be replaced.

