11.1.3 Methods for Evaluation of Measurable Disease

All measurements should be taken and recorded in metric notation using a ruler or calipers. All baseline evaluations should be performed as closely as possible to the beginning of treatment and never more than 4 weeks before the beginning of the treatment.

The same method of assessment and the same technique should be used to characterize each identified and reported lesion at baseline and during follow-up. Imaging-based evaluation is preferred to evaluation by clinical examination unless the lesion(s) being followed cannot be imaged but are assessable by clinical exam.

Clinical lesions Clinical lesions will only be considered measurable when they are superficial (e.g., skin nodules and palpable lymph nodes) and ≥ 10 mm diameter as assessed using calipers (e.g., skin nodules). In the case of skin lesions, documentation by color photography, including a ruler to estimate the size of the lesion, is recommended.

Chest x-ray Lesions on chest x-ray are acceptable as measurable lesions when they are clearly defined and surrounded by aerated lung. However, CT is preferable.

Conventional CT and MRI This guideline has defined measurability of lesions on CT scan based on the assumption that CT slice thickness is 5 mm or less. If CT scans have slice thickness greater than 5 mm, the minimum size for a measurable lesion should be twice the slice thickness. MRI is also acceptable in certain situations (e.g. for body scans).

Use of MRI remains a complex issue. MRI has excellent contrast, spatial, and temporal resolution; however, there are many image acquisition variables involved in MRI, which

greatly impact image quality, lesion conspicuity, and measurement. Furthermore, the availability of MRI is variable globally. As with CT, if an MRI is performed, the technical specifications of the scanning sequences used should be optimized for the evaluation of the type and site of disease. Furthermore, as with CT, the modality used at follow-up should be the same as was used at baseline and the lesions should be measured/assessed on the same pulse sequence. It is beyond the scope of the RECIST guidelines to prescribe specific MRI pulse sequence parameters for all scanners, body parts, and diseases. Ideally, the same type of scanner should be used and the image acquisition protocol should be followed as closely as possible to prior scans. Body scans should be performed with breath-hold scanning techniques, if possible.

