11.1.4 Response Criteria

11.1.4.1. Evaluation of Target Lesions

Complete Response (CR): Disappearance of all target lesions. Any pathological lymph nodes (whether target or non-target) must have reduction in short axis to <10 mm.

Partial Response (PR): At least a 30% decrease in the sum of the diameters of target lesions, taking as reference the baseline sum diameters.

Progressive Disease (PD): At least a 20% increase in the sum of the diameters of target lesions, taking as reference the smallest sum on study (this includes the baseline sum if that is the smallest on study). In addition to the relative increase of 20%, the sum must also demonstrate an absolute increase of at least 5 mm. (Note: the appearance of one or more new lesions is also considered progression).

Stable Disease (SD): Neither sufficient shrinkage to qualify for PR nor sufficient increase to qualify for PD, taking as reference the smallest sum diameters while on study.

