12. STATISTICAL CONSIDERATIONS

12.1 Study Design/Endpoints

With the advent of genomic profiling and targeted therapies, focusing on patients with a specific target (or genomic alteration) of interest regardless of disease type or histology is a new paradigm that cancer research is beginning to adopt. This is a Phase-2, "basket" study for patients with advanced cancers (stage 4, any histology) who have disease progression with at least one prior regimen, identified with predefined genomic alterations. Two separate cohorts will be accrued in parallel, defined by genomic *FGFR*, as well as *KIT*, *PDGFR α* , *ABL1*, *RET*, and *FLT3* alterations.

Cohort A will consist of patients identified with activating mutations or fusions in *FGFR* as well as patients with *FGFR* amplifications.

Cohort B will consist of patients identified with rare gene targets (*KIT*, *PDGFR α* , *RET*, *ABL1*, and *FLT3* alterations) for whom there may be downstream targeting and efficacy associated with ponatinib.

Our goal is to assess efficacy outcomes in these two cohorts when treated with ponatinib.

(a) Definition of primary outcome/endpoint:

The primary endpoint for each of the cohort in this study is overall response. Overall response is defined as the number of patients who achieve any response in the first 6 cycles of treatment. All eligible patients, selected by a CLIA approved assay, who have received at least one dose of ponatinib will be evaluable for response. Response for tumors would be assessed using the RECIST 1.1 criteria (using CT scans or calipers by clinical exam) where response will be defined as a partial or complete response.

(b) Definition of secondary outcomes/endpoints:

- Toxicity is defined as adverse events that are classified as either possibly, probably, or definitely related to study treatment per NCI CTCAE v4.0
- Overall survival is defined as the time from treatment initiation to death.
- Progression-free survival defined as the time from treatment initiation to progression or death

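### Section 11.1.2 lets irradiated lesions serve as target lesions without documented growth since radiotherapy, so delayed radiation shrinkage could be scored as a ponatinib response

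*Combined protocol and SAP*

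**What the plan says.** The note on irradiated lesions in Section 11.1.2 reads: "Tumor lesions that are situated in a previously irradiated area may be considered measurable". Nothing is attached about growth or progression after radiotherapy.

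The same section draws target lesions from "All measurable lesions up to a maximum of 2 lesions per organ and 5 lesions in total", so an irradiated lesion that meets the size limit can be a target. Section 11.1.4.1 defines partial response as "At least a 30% decrease in the sum of the diameters of target lesions", measured against baseline.

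Three timing rules bear on this:

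- Exclusion 3.2.24 bars "targeted therapy or radiotherapy within 4 weeks (6 weeks for nitrosoureas or mitomycin C) or within 5 half-lives, whichever is shorter" before study entry. A half-life has no meaning for radiotherapy, so 4 weeks applies.
- Section 11.1.3 sets the outer limit for baseline evaluations as "never more than 4 weeks before the beginning of the treatment". The same sentence asks for them as near to the start of treatment as can be managed.
- Section 4.1 says "Following registration, patients should begin protocol treatment within 5 business days".

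The only progression requirement is at patient level. Section 12.1 describes patients "who have disease progression with at least one prior regimen", and 3.1.1 asks for refractory metastatic disease. Neither refers to a particular lesion or to the time since radiotherapy.

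For Cohort A, Section 12.2 requires at least 1 response in the first 10 patients to continue and at least 4 in 30 to declare activity. The null response rate is 5% and the target rate 20%.

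**The concern.** In a single-arm trial with response as the primary endpoint, every counted response is credited to the drug. If a lesion was irradiated shortly before the baseline scan, and radiation can go on shrinking it afterwards, the fall in the target sum is not due to ponatinib alone. No control arm would show this.

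Section 12.2 treats 5% as the rate that chance alone would give, which leaves little room for a second source of responses. One extra response matters when the count sits at a threshold: 0 against 1 of 10 at stage 1, or 3 against 4 of 30 at the end.

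**Working it through.** **1. Can the baseline scan fall close to the end of radiotherapy?** Call first dose day 0. The scan may be as early as day −28 (11.1.3). Radiotherapy must end at least 28 days before entry (3.2.24). If entry and first dose fall on the same day, radiotherapy may end on day −28, the day of the earliest permitted scan. If registration counts as entry and dosing follows 5 business days (about 7 calendar days) later, radiotherapy ends by day −35, 7 days before that scan. At the early edge of the window the gap is thus about 0 to 7 days. With a scan just before first dose it is at least 4 weeks.

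**2. How much must the irradiated lesion shrink?** Let w be the share of the baseline target sum that lies in treated fields, with all other targets unchanged. A 30% fall in the sum needs a fall of 0.30/w in that share.

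| Share w | Shrinkage needed |
|---|---|
| 1 (only target) | 30% |
| 1/2 | 60% |
| 1/3 | 90% |
| 1/5 (one of five equal targets) | 150%, impossible |

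If the other targets do not shrink, w must be at least 0.30. The risk therefore lies mainly in patients with one or few target lesions.

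**3. Reproduce the plan's design.** For response probability p,

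P(declare) = Σ over x ≥ 1 of Bin(x; 10, p) × P(Y ≥ 4 − x), with Y ~ Bin(20, p).

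At p = 0.05 the terms are:

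- x = 1: 0.3151 × 0.0755 = 0.0238
- x = 2: 0.0746 × 0.2642 = 0.0197
- x = 3: 0.0105 × 0.6415 = 0.0067
- x ≥ 4: 0.0010

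The sum is 0.0513, marginally above the stated 5%. At p = 0.20 the result is 0.814, which meets the stated power of at least 80%. The chance of passing stage 1 under the null is 1 − 0.95^10 = 0.401.

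**4. Add spurious responses.** Let δ be the percentage points added to the 5% null rate. The documents give no value, so a range is shown.

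| δ (assumed) | p | False-positive rate | P(pass stage 1) |
|---|---|---|---|
| 0 | 0.050 | 5.1% | 0.401 |
| 0.1 | 0.051 | 5.4% | 0.408 |
| 0.5 | 0.055 | 6.8% | 0.432 |
| 1 | 0.060 | 8.7% | 0.461 |
| 2 | 0.070 | 13.2% | 0.516 |

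**5. What the range implies.** Suppose a share s of patients has an irradiated lesion large enough to drive the sum, and a share f of these shows enough delayed shrinkage. Then δ = 0.95 × s × f.

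- s = 5%, f = 2%: δ = 0.095 points, false-positive rate 5.4%
- s = 10%, f = 5%: δ = 0.475 points, 6.7%
- s = 20%, f = 10%: δ = 1.9 points, 12.7%

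All values of s and f are illustrations.

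**6. One spurious response for certain.** If exactly one of 30 patients is a spurious responder and the other 29 respond at 5%, the chance of declaring activity is 0.175 with that patient in stage 1 and 0.135 in stage 2. Averaged over position it is (1/3)(0.175) + (2/3)(0.135) ≈ 0.149. This is conditional on the spurious response occurring; it is not an estimate of the trial's error rate.

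**The case against.** Several points on the other side stand.

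- **The mechanism is assumed.** A reader might infer that the protocol's windows prove the bias. They show only that the timing is possible. The documents nowhere say that irradiated lesions shrink by 30% after a baseline scan, or how often.
- **The worst timing is at the edge.** It needs a scan near day −28, while 11.1.3 asks for imaging close to treatment. A later scan may already contain some of the radiation effect.
- **Other rules limit the risk.** Targets number up to five and should represent all involved organs. A new lesion or unequivocal non-target progression counts as progressive disease (11.1.4.2, 11.1.4.3). Confirmation is required (11.1, 11.1.4.3). An independent expert reviews files and images together (11.1.7).
- **RECIST 1.1 is cited** in 3.1.4 and 11.1. Whether the guideline adds a condition cannot be checked from these documents. One can say only that the protocol's own text states none.

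The safeguards are incomplete. Lasting radiation shrinkage would pass a confirmation scan, and 11.1.7 tells reviewers nothing about irradiated lesions. Section 11.1.2 does state a preference among targets for cystic lesions, but none for irradiated ones.

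A reader might also conclude that a single patient decides the trial. The rule does not support that: success needs four responses, and one spurious response changes the final result only when exactly three others respond. At stage 1, if the first 10 patients are all amplification-only with no response, Section 12.2 closes accrual to that group only and continues with mutation and fusion patients.

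**Conclusion.** The gap in the text is real. Irradiated lesions may be targets with no growth condition, and the permitted timing lets the baseline precede much of any radiation effect. The consequence is a possible inflation of the false-positive rate from 5.1% to between 5.4% and 13.2%, if spurious responses add 0.1 to 2 percentage points to the null rate. That range is assumed, and the calculation uses the ordinary two-stage rule without the amplification-only exception. The documents do not support reading the upper end as the trial's actual error rate. This is a low-cost improvement to the response definition and does not show that the design fails.

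**What to change.** In Section 11.1.2, replace the unconditional note with a rule that a previously irradiated lesion may be a target lesion only if growth in that lesion after completion of radiotherapy is documented at or before the baseline scan; otherwise it is followed as non-target. To apply this, sites should record radiotherapy fields and dates, and the review in 11.1.7 can use them to flag responses driven by treated lesions.

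The cost is that patients whose only measurable lesion lies in a treated field, without documented growth, would not qualify. These are probably few, but the documents give no number, and eligible alterations are uncommon (Section 12.3 expects actionable FGFR alterations in about 5% of those screened). Sample size and decision rule do not change.
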